Entry Criteria: Male subjects 4 to 8 years of age (inclusive) with a diagnosis of DMD confirmed by complete dystrophin deficiency, an identifiable mutation of the DMD gene, or complete dystrophin gene sequencing consistent with DMD, and a clinical profile consistent with DMD. Subjects should have serum potassium within the reference range at screening. Subjects taking approved treatments that target gene mutation (eg, eteplirsen or ataluren) may be enrolled in the study if they have been on a stable dose for 30 days prior to the first dose of study drug, and plan to remain on that dose throughout the study. Subjects will be excluded if they have symptomatic cardiomyopathy; have had any previous systemic treatment with corticosteroids within 2 months prior to the Screening Visit; or treatment with immunosuppressants or mineralocorticoids in the 3 months prior to the Screening Visit. Subjects must be able to complete the 10 Meter Walk/Run test in 10 seconds or less at the Screening and Baseline Visits.	

Study Title: A Multicenter, Randomized, Parallel Group, Double Blind, Multiple Dose, Placebo Controlled Study to Assess the Efficacy and Safety of MNK-1411 in Male Subjects 4 to 8 Years of Age With Duchenne Muscular Dystrophy	
Protocol Number: MNK14112096	Type: Phase 2
Condition/Disease:	Duchenne Muscular Dystrophy
Concomitant Medications and Treatments: Subjects are not permitted to receive live or live-attenuated vaccines (with the exception of the varicella zoster vaccine, if needed per Inclusion criterion 6), systemic corticosteroids (eg, prednisone or deflazacort) for DMD, mineralocorticoids, or immunosuppressants during the study. All medications and nondrug therapies (eg, physical therapy, blood transfusions, oxygen supplementation, etc) taken from 30 days prior to the Screening Visit and throughout the study will be recorded.	
Study Drug and Treatment Administration:	
The following treatments will be administered during the 24 week Blinded Treatment Period:	

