The pharmacokinetics (PK) of MNK-1411 in DMD patients will be characterized using population PK modeling with sparse PK sampling implemented in this study. The exposure response (selected efficacy and/or safety endpoints at Week 4) relationship will be explored.	
Safety Evaluations:	
The following safety assessments will be evaluated: adverse events, medical history, physical examinations, concurrent medical conditions, height, weight, clinical laboratory tests, vital signs, electrocardiograms, and antidrug antibodies.	

Study Title: A Multicenter, Randomized, Parallel Group, Double Blind, Multiple Dose, Placebo Controlled Study to Assess the Efficacy and Safety of MNK-1411 in Male Subjects 4 to 8 Years of Age With Duchenne Muscular Dystrophy

Protocol Number: MNK14112096	Type: Phase 2
Condition/Disease:	Duchenne Muscular Dystrophy

Quality of Life/ Health Outcome Evaluations:

The following quality of life /health outcome assessment will be evaluated: Pediatric Outcomes Data Collection Instrument (PODCI).

Statistical Methods:

Analysis Populations

The following analysis populations are defined for this study:

- The Modified Intent-to-Treat (mITT) Population will include all randomized subjects who receive 1 or more doses of study drug and who contribute any efficacy data to the study.
- The Safety Population will include all subjects who receive 1 or more doses of study drug.
- The PK Population will include all subjects who provide at least 1 quantifiable concentration of ACTH₁₋₂₄ following the administration of at least 1 complete dose of study drug, and without any major protocol deviations that compromise the PK samples.

Sample Size

A total of 132 subjects will be randomized in this study (44 per treatment group). The sample size was determined using the change from baseline in the 10 Meter Walk/Run time. With 37 subjects per treatment group expected to complete the Blinded Treatment Period, the trial will have an 80% power to detect a 1 second treatment difference comparing 2 groups at a significance level of 0.05. Taking into account a dropout rate of approximately 15%, the sample size for this study will be 44 subjects per treatment arm.

Efficacy Analysis

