Unless otherwise specified, all statistical tests will be two-sided with a significance level of 0.05. Summary statistics will be provided for all study variables with descriptive statistics (number of observations, mean, SD, median, minimum, and maximum) for numerical (or continuous) variables, and frequency and percentages will be calculated for categorical variables. All data will be summarized by treatment groups as appropriate. The 2 placebo groups will be combined for all analyses. Data summary and analyses will be performed with SAS 9.4 or higher.

The primary efficacy endpoint is a change from baseline in 10 Meter Walk/Run time at Week 24. The primary statistical analysis method for the endpoint will be performed using an analysis of variance (ANOVA) model with treatment as a main factor and baseline value as a covariate.

The secondary efficacy endpoints will be analyzed using the same statistical method as that for the primary efficacy endpoint.

Additional exploratory analyses [REDACTED]
[REDACTED]

Pharmacokinetic Analysis

Population PK analysis for MNK-1411 will be conducted using nonlinear mixed effects modeling.

Safety Analysis

Treatment-emergent adverse events and serious adverse events will be summarized using the appropriate version of MedDRA by preferred term within system organ class. Other safety data will be listed and summarized descriptively or graphically, as appropriate.

Study Title: A Multicenter, Randomized, Parallel Group, Double Blind, Multiple Dose, Placebo Controlled Study to Assess the Efficacy and Safety of MNK-1411 in Male Subjects 4 to 8 Years of Age With Duchenne Muscular Dystrophy

Protocol Number: MNK14112096	Type: Phase 2
Condition/Disease:	Duchenne Muscular Dystrophy

Quality of Life/Health Outcomes Analysis

The PODCI (sport and physical functioning domain and transfer/basic mobility domain) will be summarized at baseline and each study visit. Change from baseline to Weeks 4, 8, 12, 16, and 24 in PODCI domains also will be summarized. The change from baseline data will be analyzed using the same methods as those used for the primary efficacy endpoint.

Open Label Extension Analysis

In the Open Label Extension Period, efficacy data will be summarized at each visit. Safety data will also be summarized as appropriate.

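### Optional efficiency gain: the primary model shown in the synopsis adjusts for treatment and baseline value only; age, known for every boy before randomisation, could be prespecified as a covariate

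*Combined protocol and SAP*

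**What the plan says.** All of the relevant text is in the protocol synopsis (Section 6).

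- **Endpoint** (Efficacy Analysis): "The primary efficacy endpoint is a change from baseline in 10 Meter Walk/Run time at Week 24".
- **Model** (Efficacy Analysis): an analysis of variance "with treatment as a main factor and baseline value as a covariate", which is in effect an analysis of covariance. The visible text names no age term, other covariate or stratification factor.
- **Groups and tests** (Efficacy Analysis): "The 2 placebo groups will be combined for all analyses", so the 2:2:1:1 allocation becomes three groups of equal size. Unless otherwise specified, "all statistical tests will be two-sided with a significance level of 0.05".
- **Secondary endpoints** (Efficacy Analysis): "The secondary efficacy endpoints will be analyzed using the same statistical method as that for the primary efficacy endpoint".
- **Sample size**: "the trial will have an 80% power to detect a 1 second treatment difference comparing 2 groups at a significance level of 0.05", with 37 completers expected per group and 44 randomised per arm after allowing for about 15% dropout. No standard deviation is visible.
- **Entry Criteria**: "Male subjects 4 to 8 years of age (inclusive) with a diagnosis of DMD".

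**The concern.** Adjusting for a baseline variable that predicts the outcome removes noise from the treatment comparison. The plan already does this with the baseline value. Age is a natural further candidate because eligibility cannot be established without it. It therefore needs no extra data collection and no rule for missing values. The age range is also wide in relative terms: the oldest eligible boys are about twice the age of the youngest. Entry requires a walk/run time of 10 seconds or less, so boys of quite different ages may start with similar times.

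At stake is precision, not validity. If age carries information on Week 24 change beyond baseline time, leaving it out makes the confidence interval for each dose-versus-placebo contrast wider than it needs to be, in a trial sized for only 80% power. Because of randomisation, the adjusted contrast targets the same mean difference even if the age effect is not exactly linear. The covariate has to be named before unblinding so that the choice cannot be driven by the results.

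**Working it through.** **Inputs from the synopsis.** 37 completers per group, three groups (111 in total), a 1-second difference, two-sided 0.05 and 80% power.

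**Inputs that are assumed.** The residual SD is not visible and is back-solved below. The share of residual variance explained by age beyond treatment and baseline time (R²) is also not given, and is varied from 0 to 20%.

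**Step 1: the plan's own figures.** The dropout step reproduces: 37/(1 − 0.15) = 43.5, rounded up to 44, and 3 × 44 = 132. The 80% power cannot be reproduced from stated inputs because no SD is given. Solving a two-group t test (72 df) for the SD that gives 80% power yields 1.515 s.

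**Step 2: the planned model.** With q covariates and N = 111, the residual df are 111 − 3 − q. The variance of a two-group contrast is inflated, on average over chance covariate imbalance, by 1 + q/(111 − 3 − q − 1).

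- q = 1 (baseline): df 107, inflation 1 + 1/106 = 1.0094.
- q = 2 (baseline and age): df 106, inflation 1 + 2/105 = 1.0190.

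The standard error of a contrast is SD × √(1 − R²) × √(2/37 × inflation). Power comes from the noncentral t distribution with noncentrality 1/SE. The planned model has 80% power at SD = 1.514 s. Its SE is 1.514 × √(2/37 × 1.0094) = 0.354 s and its 95% CI half-width is 1.982 × 0.354 = 0.701 s.

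**Step 3: add age.** Worked row, R² = 5%: SE = 1.514 × √0.95 × √(2/37 × 1.0190) = 0.346 s; half-width = 1.983 × 0.346 = 0.687 s; 0.687/0.701 = 0.979.

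| R² of age | Power | CI half-width (s) | Change in CI width | Equivalent extra completers per arm |
|---|---|---|---|---|
| 0% | 79.6% | 0.705 | +0.5% | none (small loss) |
| 2% | 80.4% | 0.698 | −0.5% | 0.4 |
| 5% | 81.6% | 0.687 | −2.1% | 1.5 |
| 10% | 83.6% | 0.668 | −4.7% | 3.6 |
| 20% | 87.6% | 0.630 | −10.1% | 8.6 |

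The last column is the number of completers per arm at which the planned model reaches the same power (37.4, 38.5, 40.6 and 45.6), minus 37.

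**Step 4: break-even.** Power with age equals planned power at R² = 0.96%, a partial correlation of √0.0096 = 0.098.

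**Step 5: sensitivity to the back-solved SD.** If the planned model really has 85% power (SD 1.416 s), the five power figures are 84.7, 85.4, 86.4, 88.2 and 91.5%. If it has 90% (SD 1.309 s), they are 89.7, 90.3, 91.2, 92.5 and 95.0%. Break-even stays at 0.96% in both cases.

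**Step 6: cross-checks.** Simulation with 40,000 trials per setting and age uniform gave 79.5, 80.4, 81.7, 83.8 and 87.7% with age in the model. A simpler normal approximation that makes no charge for the extra covariate gives 80.0, 80.8, 82.0, 84.0 and 88.0%; the table is the more cautious version.

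**The case against.** - **Nothing in the documents shows that age is prognostic once baseline time is known.** Age appears only as an entry range. Weight, the North Star assessment and the other timed tests are also named, and no document-based ranking puts age above them. This stands. The case for age is that it is certain to be available and plausible as a predictor, and the benefit may be nil.
- **The gain is small under modest assumptions.** At R² of 2% it is 0.4 point of power, and at 5% it is 1.6 points. Gains of 3.6 points or more need R² of 10 to 20%, a partial correlation of about 0.32 to 0.45. The entry limits on age and walk/run time restrict the range of both variables. This also stands: the 0 to 5% rows deserve the most weight, and the 20% row is the optimistic end of the range, not an expectation.
- **Only a synopsis is public.** One sentence there does not show that the full statistical section lacks an age term. This is correct, and the recommendation is conditional on it.
- **The SD is inferred.** It is not known whether the planners meant the SD of raw change or the residual SD after baseline adjustment. This matters little: the relative change in CI width and the break-even do not depend on the SD.

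None of this makes adding the covariate wrong or costly. It limits how much benefit can be claimed.

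**Conclusion.** The point holds as an optional improvement, with low confidence in the size of the benefit. The planned baseline-adjusted model is valid. Adding age costs about 0.4 percentage point of power if age is uninformative (about 0.3 if planned power is really 85 or 90%). Starting from 80%, it gains 1.6 points if age explains 5% of the residual variance and 3.6 points if it explains 10%. It pays for itself once age explains about 1%.

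These figures rest on 37 completers in each of three groups, a residual SD back-solved from the stated power, and an assumed R² that the documents do not supply. The treatment effect being estimated does not change.

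**What to change.** Check the full statistical section first. If age is already in the primary model, nothing is needed. If not, state in the SAP before unblinding that change in 10 Meter Walk/Run time at Week 24 is modelled on treatment, baseline walk/run time and age at baseline, with age as a continuous linear term. The secondary endpoints inherit the primary method and may carry the same term; no gain is claimed for them.

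The cost is one sentence and one residual degree of freedom, with no new data collection and no missing-covariate rule. The statistical downside is the loss of about 0.4 point of power if age proves uninformative.
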